4.6.3.2 Time-normalized HAE attack frequency of < 1 HAE attack per 4-week Period

The number and percentage of subjects who experience less than 1 HAE attack per 4 week period (i.e. 28 days) and those who experience at least 1 HAE attack per 4 week period will be summarized. For the calculation of the HAE attacks per 4 week period the time-normalized number of HAE attacks as described in [Section 4.6.3](#) will be multiplied by 28. 95% Wilson Confidence Intervals will be calculated for all percentages.

The number of HAE attacks as well as the difference in the number of attacks experienced following treatment with CSL830 as compared to number of attacks pre-study will also be summarized.

A subgroup analysis will be performed for age (≤ 17 years / >17 years).

Subjects who have less than 1 HAE attack per 4-week period will be flagged.

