3.3 Study Schedule

3.3.1 Planned study duration

The duration of the study for an individual subject who does not participate in the Extension Period is expected to be up to 58 weeks. This estimation is based on:

- A Screening Period lasting up to 4 weeks (≤ 28 days), as needed.
- Two treatment periods totaling 52 weeks (367 days \pm 2 days).
- A Follow-up Period lasting 2 weeks (14 days \pm 3 days).

The overall study duration (i.e., from the first subject's first Screening Visit to the last subject's Follow-up Visit) is planned to be 26 months, but will depend on recruitment.

US-subjects will have the opportunity beyond the Week 53 Visit to enter into an Extension Period of up to 90 weeks. The Extension Period will comprise a treatment period of 88 weeks and a follow-up period of 14 days \pm 3 days (see Country-Specific Protocol Amendment No. 1 (United States), dated 10 July 2015).

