4.4 Baseline and Demographic Characteristics

Subject characteristics and medical history will be presented in summary tables for the ITT and Safety Populations as described in [Section 4.1](#).

This will include:

- Demographics (age [years], sex, race, ethnicity, height, body weight, and body mass index [BMI; calculated as kg/m²]).
- Medical history (relevant medical history for the previous 6 months, contraception method [if relevant]) and the correspondent therapies which have an end date on or after the date of the first study treatment (current therapies). Medical history will be presented by system organ class (SOC) and preferred term (PT), and will be classified using version 18.0 of the Medical Dictionary for Regulatory Activities (MedDRA). Current Therapies will be presented by Anatomical Therapeutic Chemical (ATC) class and PT.
- HAE history (including confirmation of HAE diagnosis, identification of HAE type, and number of HAE attacks in the 3 months before the Screening visit) and Medical HAE History (any prior prophylactic therapy relating to HAE during previous 3 months for “CSL830-Naïve” Subjects).

The relevant medical history for the previous 6 months will include all medical history of subjects during the previous 6 months before Screening. The confirmation of HAE diagnosis, identification of HAE type, and number of HAE attacks in the 3 months before Screening will be presented.

The number of HAE attacks in the 3 months before the Screening Visit will also be displayed as the rate of HAE attacks before the Screening Visit per month. Therefore, the number of HAE attacks in the 3 months before the Screening Visit will be divided by 3.

For “CSL830-Naïve” Subjects and “CSL830-Interrupted” Subjects screening is the Screening Visit of study CSL830_3002. For “CSL830-Continuation” Subjects, screening is the Screening Visit of study CSL830_3001. Information in the medical history will be updated if any changes occurred in the course of study CSL830_3001.

The label “Any Prior Prophylactic Therapy Related to HAE During Previous 3 Months” in the HAE history and medical HAE history table will only include therapies taken within 3 months prior to Screening of Study CSL830_3002. Prior therapies before Screening of study CSL830_3001 will not be included. Consequently, only “CSL830-Naïve” Subjects will have data in this part of the table.

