4.6 Efficacy Analysis

The secondary efficacy analyses will be carried out for the ITT and PP Populations. The ITT Population is used as the primary analysis and the Per Protocol Population will be used as secondary analysis.

The evaluation period for efficacy assessments will be from the start (Day 1) of Week 3 of a treatment in Treatment Period 1 until the End of Study Visit (Week 53 Visit) or the last administration of CSL830 + 4 days (whichever occurs first) for subjects who are not participating in the Extension Period. For subjects who are taking part in the Extension Period, the evaluation period will be from the start (Day 1) of Week 3 of the treatment in Treatment Period 1 until the End of Study Visit of the Extension Period (Week 88) or the last administration of CSL830 + 4 days (whichever occurs first). For subjects who are participating in the Extension Period and who have a rest period between Treatment Period 2 and the Extension Period, the evaluation period will exclude the rest period between the Week 53 Visit or the last administration of CSL830 + 4 days (whichever occurs first) of Treatment Period 2 and the first visit of the Extension Period.

CCI

Each day, subjects are to enter HAE symptoms (yes/no) into their eDiary and, if yes, the severity(s) and location(s) of the HAE symptom(s). Investigator-reported HAE attacks are based upon review of patient diaries and review of relevant interim medical history, including hospital/medical records and any information provided by the subject. Using medical judgment, the investigator is to determine the occurrence of an HAE attack and report its start and stop dates (generally from onset of the first symptom preceded by symptom-free day to the last symptom preceding symptom-free day), its severity (based upon maximal intensity of any symptom as judged by the investigator), and its location(s) (all involved locations as judged by the investigator are to be reported). Each HAE attack is to be preceded and followed by an attack-free day. For every visit, the Investigator is to report all HAE attacks that have occurred in the interim since the last visit the subject attended.

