4.6.3 Secondary efficacy endpoints

Secondary efficacy endpoints are:

- a. The percentage of subjects who are responders. The “response” is defined as a $\geq 50\%$ relative reduction in the time-normalized number of HAE attacks during treatment with CSL830, compared with the time-normalized number of attacks that is used to qualify the subject for participation in this study (see Section 4.1.2 of the protocol [inclusion criterion 5]).
- b. The percentage of subjects who experience a time-normalized number of HAE attacks of < 1 HAE attack per 4-week period.

The time-normalized number of HAE attacks during treatment with CSL830 is calculated per subject as:

- The number of HAE attacks /length of stay of subject (days);

where the length of stay for subjects who are not participating in the Extension Period is calculated as:

- Date of End of Study Visit at Week 53, date of the 4th day post the last IMP administration or study discontinuation date (whichever occurs first) – date of Day 1 Week 3 + 1.

for HAE attacks with start date before (including) the Week 53 visit, the last administration of CSL830 + 4 days or study discontinuation date (whichever occurs first).

For subjects who are continuing into the Extension Period and have no rest period, the length of stay is calculated as:

- Date of End of Study Visit at Week 88, date of the 4th day post the last IMP administration or study discontinuation date (whichever occurs first) – date of Day 1 Week 3 + 1.

for HAE attacks with start date before (including) the Week 88 visit, the last administration of CSL830 + 4 days or study discontinuation date (whichever occurs first).

For subjects who are continuing into the Extension Period and have a rest period, the length of stay is calculated as:

- {Date of End of Study Visit at Week 53, date of the 4th day post the last IMP administration in Treatment Period 2 (whichever occurs first) – date of Day 1 Week 3 + 1} + {Date of End of Study Visit at Week 88, date of the 4th day post the last IMP administration in the Extension Period or study discontinuation date (whichever occurs first) – date of first visit of the Extension Period + 1}.

for HAE attacks with start date outside the rest period and before (including) the Week 88 Visit or the last administration of CSL830 + 4 days or study discontinuation date (whichever occurs first).

HAE attacks with start dates

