- between one day after the End of Study Visit or 4th day post last IMP administration [whichever occurs first] and the Follow-up Visit of Treatment Period 2 (applicable for subjects not participating in the Extension Period)
- between one day after the End of Study Visit or 4th day post last IMP administration [whichever occurs first] and the Extension Follow-up Visit (applicable for subjects participating in the Extension Period)
- between one day after the Week 53 Visit or 4th day post last IMP administration [whichever is first] of Treatment Period 2 and the first visit of the Extension Period (applicable for subjects who are taking part in the Extension Period and who have a rest period)

will not be included in the analyses (ie the numerator “number of HAE attacks”).

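### The SAP 4.6.3.2 change-from-pre-study summary is worded as a difference of attack counts over very unequal windows, with the pre-study window unnamed; it should be stated per 28 days

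*SAP*

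**What the plan says.** SAP 4.6.3.2 concerns the percentage of subjects with fewer than one attack per 4 weeks. For that endpoint the scaling is explicit: "For the calculation of the HAE attacks per 4 week period the time-normalized number of HAE attacks as described in" Section 4.6.3 is multiplied by 28. A separate sentence then adds a summary of the number of attacks and of "the difference in the number of attacks experienced following treatment with CSL830 as compared to number of attacks pre-study". That sentence carries no scaling and no reference to a pre-study window.

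Elsewhere the SAP keeps count and rate apart. Section 4.6.3 defines the time-normalized number as "The number of HAE attacks /length of stay of subject (days" (the bracket closes there). The same section says of attacks that start outside the window that they "will not be included in the analyses (ie the numerator “number of HAE attacks", so the unqualified number is the numerator. Section 4.6.3.1, the responder endpoint, uses the time-normalized number on both sides of its comparison.

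Two pre-study counts are available. Section 4.6.3.1 uses the attacks that qualified the subject, at least 4 in 2 months. Section 4.4 uses a 3-month history: "The number of HAE attacks in the 3 months before the Screening Visit will also be displayed as the rate" per month, after division by 3.

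**The concern.** A difference between two counts measures drug effect only if the two windows are of similar length. Here one window is 2 or 3 months and the other is about one year or more than two and a half years. The literal quantity therefore largely tracks length of follow-up. It can show an increase in attacks for a subject whom Section 4.6.3.1 classes as a responder.

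The result would not stay in a listing. SAP 4.1 gives continuous efficacy variables a mean with 95% CI by dose group. SAP 4.1 and 4.14 analyse Extension and non-Extension subjects together, and Protocol 3.5 expects about 50 Extension subjects against 100 planned completers.

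The unnamed window adds a second ambiguity. For CSL830-Interrupted subjects, Section 4.4 counts the 3 months before Screening for this study, which can overlap treatment in CSL830_3001. Section 4.6.3.1 counts attacks before Screening for CSL830_3001. Two programmers could produce different tables from the same sentence.

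**Working it through.** The plan gives no figure for this summary, so there is none to reproduce. The check is of window lengths and of what the literal formula returns.

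**On-treatment window (full completers).** Start: "The evaluation period for efficacy assessments will be from the start (Day 1) of Week 3 of a treatment in Treatment Period 1" (SAP 4.6), which is study Day 15. End without the Extension: the Week 53 Visit, Day 367 (SAP 3.3.1: "Two treatment periods totaling 52 weeks (367 days", ±2). End with the Extension: Week 88, which is Extension Day 617 in the Protocol's Extension schedule. With no rest period, Extension Day 1 is Day 367, so the end is 367 + 616 = Day 983.

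- No Extension: 367 − 15 + 1 = 353 days
- Full Extension: 983 − 15 + 1 = 969 days (353 + 617 = 970 with a rest period)
- Ratio of the two: 969 / 353 = 2.7

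**Pre-study window.** Assuming 30.44 days per month: 2 months = 60.9 days, 3 months = 91.3 days.

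**Literal difference.** Raw difference = pre-study rate × (1 − fall) × on-treatment days − pre-study count. It is negative only if the fall exceeds 1 − (pre-study days / on-treatment days). The illustration assumes 4 attacks in 2 months, or the same monthly rate (6 attacks) over 3 months.

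| Pre-study count | On-treatment days | Window ratio | Fall needed for a negative difference | Raw difference, rate unchanged | Raw difference, 50% fall |
|---|---|---|---|---|---|
| 4 in 2 months | 353 | 5.8 | about 83% | 23.2 − 4 = +19.2 | 11.6 − 4 = +7.6 |
| 4 in 2 months | 969 | 15.9 | about 94% | 63.7 − 4 = +59.7 | 31.8 − 4 = +27.8 |
| 6 in 3 months | 353 | 3.9 | 74.1% | 23.2 − 6 = +17.2 | 11.6 − 6 = +5.6 |
| 6 in 3 months | 969 | 10.6 | 90.6% | 63.7 − 6 = +57.7 | 31.8 − 6 = +25.8 |

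The falls in the fourth column do not depend on the count. A 50% fall is exactly the responder threshold.

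**Per-28-day scale.** 4 / 60.9 × 28 = 1.84 before. After a 50% fall the rate is 0.92, a difference of −0.92 in all four rows.

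**Pooling.** At a 50% fall and the 2-month count, each 10 percentage points of difference in Extension share between dose groups moves the mean by 0.10 × (27.8 − 7.6) = 2.0 attacks, with no difference in rate.

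**Sign by Extension status.** With 4 qualifying attacks the raw difference is zero at 4 × 28 / 353 = 0.32 attacks per 28 days without the Extension and at 4 × 28 / 969 = 0.12 with it. Opposite signs arise only between these rates. At 0.2 per 28 days the differences are 2.5 − 4 = −1.5 and 6.9 − 4 = +2.9. At 0.5 they are 6.3 − 4 = +2.3 and 17.3 − 4 = +13.3, the same sign.

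**Short follow-up.** For a subject with 28 days and an unchanged rate, the difference is 1.84 − 4 = −2.2, so the distortion reverses.

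**The case against.** The strongest reply is that this is loose wording rather than a plan to subtract raw counts. The section heading speaks of a time-normalized frequency, and the summary closely follows the ×28 rule, so a programmer could carry the scaling over. The table shells are in a separate document. The revision history names a time-normalized number of attacks as an endpoint in its own right, and its definition may lie in the blacked-out exploratory sections. This part stands: the documents do not show that raw counts would be tabulated. It does not cure the sentence. The ×28 rule is stated for a different quantity, and Section 4.6.3 uses the unqualified term for the numerator.

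It can also be said that the qualifying attacks are the natural comparator, since Section 4.6.3.1 and Protocol 10.1 both use them. That is fair, but Section 4.6.3.2 does not refer to them.

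A reader might infer that Extension and non-Extension subjects with the same attack rate would show opposite signs. The arithmetic does not support this in general: it happens only in the band of about 0.12 to 0.32 attacks per 28 days, for 4 qualifying attacks. A reader might also take 353 to 969 days as the range for everyone. It is not. SAP 4.6.3 closes the window at last dose + 4 days or at discontinuation if earlier, and Protocol 3.3 lets Extension subjects near the study end take the final visit early and still count as completers.

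**Conclusion.** The point holds as a defect of specification with a material effect if followed literally. By the SAP's own terms the summary is a difference of counts. For full completers its sign would follow the treatment effect only for falls in rate above about 83% or 94% against the 2-month count, or 74.1% and 90.6% against the 3-month count. Pooled means would vary with Extension participation. These figures assume full follow-up and 30.44-day months; the attack differences also assume the minimum qualifying count, or the same monthly rate over 3 months.

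A reader might infer that the trial's efficacy conclusions are at risk. They are not. The study has no primary efficacy analysis, the primary endpoints are safety rates, and both secondary efficacy percentages are explicitly time-normalized. The affected item is one supplementary descriptive summary. It is worth correcting because it could contradict the responder result for the same subject.

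**What to change.** Replace the sentence in SAP 4.6.3.2 with: *the time-normalized number of HAE attacks per 28 days on CSL830 and its difference from the time-normalized number (per 28 days) of the qualifying attacks used in Section 4.6.3.1 will also be summarized.* This settles the scale and the comparator together. Make the table shell match.

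The cost is one sentence and a check of one shell. All inputs are already collected and already used for the responder endpoint.

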4.7 Safety Analysis

Safety endpoints will be analyzed using the Safety Population as described in [Section 4.1](#).

AE will be classified using the Medical Dictionary for Regulatory Activities (MedDRA) version 18.0.

AEs which have a start date and time on or after the first injection date and time of CSL830 in study CSL830_3002 are considered treatment-emergent AEs. AEs with missing or partial start date or time will also be considered treatment-emergent following the worst case principle unless the partial date clearly indicates that the AE started before first injection date and time.

Only treatment-emergent AEs will be summarized in tables as described in [Section 4.1](#). AEs occurring after the Week 53 Visit and before the Follow-up Visit of Treatment Period 2 or the first visit of the Extension Period will be assigned to Treatment Period 2. AEs occurring between the Extension Period completion visit and the Extension Period Follow-up Visit will be assigned to the preceding treatment of the Extension Period.

Subgroup analyses will be performed for

- Use of any oral Prophylaxis for Treatment of HAE during the study
- Subject roll-over classification (“CSL830-Continuation” Subjects, “CSL830-Interrupted” Subjects, and “CSL830-Naïve” Subjects)

The subgroup “Subjects who use oral agents for the prophylactic treatment of HAE during the study” will only include subjects who are taking their prophylaxis according to protocol.

Notes:

- The above described subgroup analyses will only be done for
 - the overall AE tables for summary measures of safety
 - the primary safety endpoints by actual treatment
- Categories of subgroups will be presented in tables only if there are a minimum number of subjects in the subgroup ($n \geq 5$).
- If a causality assessment is not provided for an AE, that AE will be considered related to the investigational product. A subject having related and unrelated AEs will be counted once in each category, related and unrelated.
- Missing severity or outcome will be classified as “severe” or “not recovered”, respectively.
- A subject having AEs with different severities will be counted once in each severity category.
- A subject with more than one occurrence of the same AE PT will be counted once in the total count for that AEs PT. Similarly, a subject with one or more AEs in a particular SOC will be counted once in the total for that SOC.

4.7.1 Primary Safety Analysis

Primary safety endpoints are listed in [Section 2.1](#).

The date of study completion is defined for the safety analyses as the (latest) Follow-up Visit. If a subject discontinued from the study, the date the subject came back to site for a final

study visit will be entered as the date of study discontinuation (to be entered as Week 53 Visit for subjects not taking part in the Extension Period and to be entered as Week 88 Visit for subjects taking part in the Extension Period) or if no further study visit takes place, the date when the subject informed the investigator. The study completion or study discontinuation (whichever applies for the individual subject) is considered as the end of treatment date.

The person-time incidence rates will be calculated in two different ways:

- For the number of subjects experiencing a particular event (bullet points i. below),
- For the number of experienced events (bullet points ii. below).

These 2 analyses approaches for the primary safety endpoints are conducted using 3 different approaches for the selection of the treatment groups which are included in the respective analyses. The following treatment groups will be regarded:

- 1) Treatment, as treated, up until CSL830 dose increase, or either CSL830 discontinuation or study completion – whichever comes first.
- 2) Treatment, as treated at the time of randomization, up to CSL830 discontinuation or study completion – whichever comes first.
- 3) Actual treatment.

In total, six analyses will result and the person-time incidence rates will be calculated

for 1) as

- i. the number of subjects experiencing a given primary endpoint safety event during the treatment duration with CSL830 up until the time of CSL830 dose increase or either CSL830 discontinuation or study completion (whichever is first), divided by the sum of each subject's time at risk. The "time at risk" (in years) is calculated per subject as:

(Date the subject experiences the first event or a CSL830 dose increase or either CSL830 discontinuation or study completion (whichever is first) – date of the subject's first injection of CSL830 in treatment + 1) / 365.25.

- ii. the sum of each subject's total number of events of a given primary endpoint safety event during the treatment duration with CSL830 up until the time of CSL830 dose increase or either CSL830 discontinuation or study completion (whichever is first), divided by the sum of each subject's time at risk. The "time at risk" (in years) is calculated per subject as:

(Date the subject undergoes CSL830 dose increase or either CSL830 discontinuation or study completion (whichever is first) – date of the subject's first injection of CSL830 in treatment + 1) / 365.25.

A subject accrues events from the subject's first CSL830 dose until the subject's first CSL830 dose change (i.e., CSL830 dose increase or either CSL830 discontinuation or study completion, whichever is first). If a subject undergoes a dose increase and such subject experiences events after the dose increase, such events are not included in this analysis. Only events which start under the dose as assigned at the time of randomization are included.

for 2) as

- i. the number of subjects experiencing a given primary endpoint safety event up until the time of CSL830 discontinuation or study completion (whichever is first), divided by the sum of each subject's time at risk in the study. The "time at risk" (in years) is calculated per subject as:

(Date the subject experiences the first event or either CSL830 discontinuation or study completion (whichever is first) – date of the subject's first injection of CSL830 in treatment + 1) / 365.25

- ii. the sum of each subject's total number of events of a given primary endpoint safety event up until the time of CSL830 discontinuation or study completion, divided by the sum of each subject's time at risk. The "time at risk" (in years) is calculated per subject as:

(Date the subject undergoes CSL830 discontinuation or study completion (whichever is first) – date of the subject's first injection of CSL830 in treatment + 1) / 365.25

A subject accrues events by treatment group, as treated at time of randomization, from the subject's first CSL830 dose until the subject undergoes CSL830 discontinuation or study completion. If a subject undergoes a dose increase and such subject experiences events after the dose increase, such events are included and attributed to the CSL830 treatment at time of randomization.

for 3) as

- i. the number of subjects experiencing a given primary endpoint safety event during treatment with an actual dose of CSL830 divided by the sum of each subject's time at risk while receiving that actual dose of CSL830. The "time at risk" (in years) is calculated per subject as:

(Date the subject experiences the first event, a CSL830 dose increase, or either CSL830 discontinuation or study completion (whichever is first) while taking a given, actual dose of CSL830 – date of the subject's first injection of the given, actual dose of CSL830 + 1)] / 365.25.

- ii. the sum of each subject's total number of events of a given primary endpoint safety event during treatment with an actual dose of CSL830 divided by the sum of each subject's time at risk while receiving that actual dose. The "time at risk" (in years) is calculated per subject as:

(Date the subject undergoes CSL830 dose increase or either CSL830 discontinuation or study completion (whichever is first) while taking the given, actual dose of CSL830 – date of the subject's first injection of the given, actual dose of CSL830 + 1)] / 365.25.

A subject accrues events over the time during which that subject receives a given actual CSL830 dose while participating in the study. If a subject undergoes a dose increase during the study and that subject experiences events during treatment with each respective dose of CSL830, such a subject contributes events in each treatment received. A subject randomized to 40 IU/kg and up-titrated to 60 IU/kg will be displayed in both treatments as well as in the ≥ 40 IU/kg treatment based upon their corresponding duration in that treatment.

The 95% CI will be calculated for each of the above described person-time incidence rates using the following formula:

$$\text{Lower CI} = \frac{k}{T} \chi^2(2 * Y, 0.025)/2$$

$$\text{Upper CI} = \frac{k}{T} \chi^2(2 * Y + 2, 0.975)/2$$

with

k = factor to normalize for annual rate which is equal to 1

T = sum of time at risk [years] over subjects calculated as described in the bullet points above.

For the person-time incidence rates described above in i.:

Y = number of subjects who experienced the safety event

For the person-time incidence rate described above in ii.:

Y = number of safety events

A by-subject listing will be produced showing the information if a subject has each primary endpoint safety event.

